3.2 Selection of Study Population

The study population will include approximately 333 primary eyes of up to 333 subjects who meet all eligibility criteria. Potential subjects who meet all eligibility criteria will be offered consecutive enrollment in the study. Enrolled subjects will have surgery to implant study lenses in either one or both eyes. For subjects who qualify to participate bilaterally, fellow eye implantation will occur between 7 days and 14 days after uneventful surgery in the first eye. If, in an Investigator's medical judgment, second eye surgery should be postponed to a date more than 14 days from primary eye implantation due to a safety concern, the Medical Monitor's approval for second eye surgery will be required.

3.2.1 Eligibility

3.2.1.1 Inclusion Criteria

This study will include subjects or eyes meeting the following criteria:

1. Subjects 21 through 45 years old at time of surgery.
2. For EVO/EVO+ ICL for Myopia:
 - Moderate to high myopia ranging from -3.00 D to \leq -20.00 D spherical equivalent (SE) in the spectacle plane with less than or equal to 2.50 D of astigmatism (in the spectacle plane).

For EVO/EVO+ Toric ICL for Myopia with Astigmatism:

- Moderate to high myopic astigmatism with spherical equivalent ranging from -3.00 D to \leq -20.00 D (in the spectacle plane) and cylinder in the range of 1.00 D to 4.00 D (in the spectacle plane).
 - Stable refractive history within 0.50 D cylinder for 1 year prior to implantation as determined by the Investigator.
3. Stable refractive history within 0.50 D for spherical equivalent 1 year prior to implantation as determined by the Investigator.
 4. For a subject who is expected to have residual postoperative cylindrical refractive error of \geq 1 D (as determined by STAAR Online Calculation and Ordering Software, OCOS), the subject should be given the opportunity to experience his/her vision with the anticipated correction.

5. Anterior chamber depth (ACD) 3.00 mm or greater, when measured from the corneal endothelium to the anterior surface of the crystalline lens.
6. Meet minimum ECD requirements for age and ACD (refer to the “Minimum ECD for Age and True ACD*” table below).
7. CDVA to at least 20/40 in the eye(s) to be treated; and absent of ocular pathology (except that myopic degeneration is allowed).
8. Difference between cycloplegic refraction spherical equivalent (CRSE) and manifest refraction spherical equivalent (MRSE) of < 0.75 D.
9. For current contact lens wearers, stable MRSE (within ± 0.5 D) on two consecutive examination dates with stability of the refraction determined by the following criteria:
 - Discontinuation of contact lens use for at least 2 weeks (rigid contact lenses and all toric contact lenses) or 3 days (non-toric soft contact lenses) prior to the first refraction;
 - Two refractions performed at least 7 days apart.
10. Able and willing to return for scheduled follow-up examinations after surgery.
11. Subjects must be able to read, understand and provide written informed consent on the IRB approved ICF and provide authorization as appropriate for local privacy regulations.

3.2.1.2 Exclusion Criteria

This study will exclude subjects or eyes meeting the following criteria:

1. Younger than 21 or older than 45 years of age.
2. With true ACD < 3.00 mm*.
3. Anterior chamber angle less than Grade III as determined by gonioscopic examination.
4. Do not meet the minimum ECD as defined in the “Minimum ECD for Age and True ACD*” table below.
5. Coefficient of variation (CV) of endothelial cell area of > 0.45 .
6. Percent hexagonality (% hex) of endothelial cell shape ≤ 45 %.
7. Unstable or worsening nearsightedness.
8. Ocular hypertension or glaucoma.
9. Pseudoexfoliation.
10. Pigment dispersion.
11. History or clinical signs of iritis/uveitis.
12. Insulin-dependent diabetes or diabetic retinopathy.
13. History of previous ocular surgery.

14. Cataract of any grade.
15. Progressive sight threatening disease or other previous or current ocular conditions, other than myopia or myopic degeneration, which may predispose for future complication in either eye.
16. Serious acute, chronic or systemic, non-ophthalmic disease or illness that would increase the operative risk, confound the outcome(s) of the study or which may preclude study completion (e.g., immunocompromised, connective tissue disease, clinically significant atopic disease, uncontrolled diabetes, etc.).
17. Monocular subjects.
18. For EVO/EVO+ ICL for myopia: myopia less than -3.00 D SE (in the spectacle plane) or greater than -20.00 D SE (in the spectacle plane) and/or with greater than 2.50 D of astigmatism (in the spectacle plane).
19. For EVO/EVO+ Toric ICL for myopia with astigmatism: myopia less than -3.00 D or greater than -20.00 D SE (in the spectacle plane) and/or refractive cylinder (in the spectacle plane) less than 1.00 D and greater than 4.00 D.
20. Pregnant or nursing women, or those who plan to become pregnant over the course of this clinical study or has another condition with associated fluctuation of hormones that could lead to refractive changes.
21. Involved in another clinical study or who may have been involved in a different clinical study within 30 days prior to this clinical study or will be involved in a different clinical study while participating in this study.
22. Subjects who, in the judgment of the Investigator, present any emotional, physiologic, or anatomical condition which may preclude participation in this study or provide an inappropriate landscape for the intended study treatment.

Minimum Endothelial Cell Density for Age and True ACD*

Age	Minimum ECD ACD ≥ 3.0 mm	Minimum ECD ACD ≥ 3.2 mm	Minimum ECD ACD ≥ 3.5 mm
21-25	3875 cells/mm ²	3800 cells/mm ²	3250 cells/mm ²
26-30	3425 cells/mm ²	3375 cells/mm ²	2900 cells/mm ²
31-35	3025 cells/mm ²	2975 cells/mm ²	2625 cells/mm ²
36-40	2675 cells/mm ²	2625 cells/mm ²	2350 cells/mm ²
41-45	2350 cells/mm ²	2325 cells/mm ²	2100 cells/mm ²
>45	2075 cells/mm ²	2050 cells/mm ²	1900 cells/mm ²

*The true ACD is defined as the distance from the apex of the posterior corneal surface to the apex of the anterior crystalline lens surface. Many measuring devices provide an ACD measurement defined as the distance from the apex of the anterior corneal surface to the apex of the anterior crystalline lens surface. If the surgeon is using an

instrument that measures from the anterior corneal surface, the thickness of the cornea must be subtracted to get the true ACD.

3.2.2 Subject Completion

The subject has completed the entire study when Postoperative Visit 8 (Day 1050 – 1170) is concluded. Subjects who require further follow-up for an AE will be followed according to Section 6.0.

3.2.3 Subject Discontinuation

A subject may be discontinued (at the discretion of the Investigator, the Sponsor and/or the IRB) prior to the final study visit for several reasons, including, but not limited to:

- voluntary withdrawal
- death
- surgical complication preventing implantation of the study lens in any eye
- explant of the study lenses

If both EVO/EVO+ study lenses are explanted, a minimum of one post-explant visit should be completed to record safety measures for the subject (e.g., CDVA, cataract/lens evaluation, endothelial cell count, etc.) prior to subject discontinuation.

Prior to discontinuing a subject, every effort should be made to contact the subject, schedule a final study visit, and obtain as much follow-up data as possible.

Adverse events will be followed as described in Section 6.0. Subject withdrawals will be documented clearly on the source document and applicable CRF.

Only subjects who do not receive any study lenses MAY be replaced. Subjects who are discontinued from the study following treatment will not be replaced.

Discontinued subjects should be followed outside of the study protocol according to the Investigator's normal postoperative standard of care.

3.2.4 Lost to Follow-up

Subjects who do not return for the final study visit, as defined by the visit window and cannot be contacted, will be considered lost to follow-up. All follow-up attempts will be documented in the subject's source documentation, and the applicable CRFs will be completed.

3.3 Investigators

- The study will be conducted at up to 20 clinical site(s) located in the US.
- The study will be conducted by Investigators who have prior clinical experience with the STAAR Surgical ICL and who are determined by STAAR Surgical to be suitably qualified by training and experience to conduct this study in compliance with all applicable Good Clinical

Practices (GCPs) and FDA Federal Regulations. Sub-Investigators will be identified on the Device Investigator Agreement (DIA)/DOA (Delegation of Authority Log).

- Each clinical site should enroll a minimum of 20 subjects and no one site can have more than 25% of the total enrollment.
- In the event that selected sites do not meet full enrollment, the Sponsor may decide to increase enrollment as needed at other currently active sites and additional site(s) may be added to satisfy the enrollment requirements of the study.

3.4 Study Duration

The duration of the study, including the time to recruit all subjects, will be approximately 46 months. Eligible subjects who are enrolled in the study will be seen for 10 scheduled study visits (per eye) over the course of approximately 3 years (1050 – 1170 days) after surgery.

4.0 STUDY MATERIALS

[figure not shown]
4.1 Description of Investigational Device

The EVO/EVO+ Visian® Implantable Collamer® Lens for Myopia, and EVO/EVO+ Visian® Toric Implantable Collamer® Lens for Myopia with Astigmatism investigational devices (EVO/EVO+ lenses), are sterile intraocular implants manufactured from Collamer, a proprietary hydroxyethyl methacrylate (HEMA)/porcine- collagen biocompatible polymer material. These lenses contain a UV absorber made from a UV absorbing material. The lenses feature a plate-haptic design with a central convex/concave optical zone and incorporate a forward vault to minimize contact with the central anterior capsule.

The EVO/EVO+ lenses feature a 0.36 mm central port, and an optic diameter that varies with the dioptric power; the smallest optic diameter being 4.9 mm and the largest 5.8 mm for EVO and 6.1 mm for EVO+. The implantable lenses are capable of being folded and inserted into the posterior chamber through an incision of 3.5 mm or less. The EVO/EVO+ lenses have orientation markings on the footplates to ensure the lenses are implanted in the correct orientation. When correctly oriented the orientation markings will be on the leading right/trailing left footplates.

[figure not shown]
The EVO/EVO+ lenses are intended to be placed entirely within the posterior chamber (ciliary sulcus) directly behind the iris and in front of the anterior capsule of the human crystalline lens. When correctly positioned, the lenses function as a refractive element to optically reduce moderate to high myopia and myopic astigmatism (toric lens only).

Figure 1: EVO/EVO+ Lens Models for Myopia

The EVO/EVO+ Toric lenses are labeled using a plus cylinder axis format. The lens axis is labeled to the nearest degree and as such lenses of any axis between 1° to 180° may be held in inventory. The EVO/EVO+ Toric Lenses are designed to be rotated up to 22.5° clockwise or counterclockwise in order to align the lens axis at the preoperative plus cylinder axis. The lenses have two engraved lines, one on each side of the optic. These are to aid with the axis alignment of the lens. The markings indicate the meridian from which the cylinder axis is measured and do not indicate the cylinder axis of the lens.

Figure 2: EVO/EVO+ Toric Lens Models for Myopia with Astigmatism

The following EVO/EVO+ Models will be included in this study:

- EVO/EVO+ Visian Implantable Collamer Lens (ICL) for Myopia:
VICMO12.1, VICMO12.6, VICMO13.2, VICMO13.7, VICM5_12.1, VICM5_12.6, VICM5_13.2, VICM5_13.7
- EVO/EVO+ Visian Toric ICL for Myopia with Astigmatism:
VTICMO12.1, VTICMO12.6, VTICMO13.2, VTICMO13.7, VTICM5_12.1, VTICM5_12.6, VTICM5_13.2, VTICM5_13.7

Refer to Table 1 for a summary of design details for the investigational EVO/EVO+ lenses in addition to the MICL and TMICL lenses currently available in the US.

Table 1: Visian ICL Device Descriptions – Approved MICL/TMICL models and Investigational EVO/EVO+ Lenses

Lens Feature	Approved in the US	Investigational Study CP19-01 EVO/EVO+ lenses	
	MICL (P030016), TMICL (P030016/S001)	VICMO, VTICMO	VICM5, VTICM5
Haptic	Single piece, plate haptic		
Material	Collamer		
Central Optic Feature	N/A	0.36 mm diameter center port (KS-AquaPORT®)	
Storage Solution	BSS		
Optic Diameters	4.9 - 5.8 mm	4.9 - 5.8 mm	5.0 - 6.1 mm
Optic Design	Spherical anterior and posterior surfaces		
Overall Lens Lengths	12.1, 12.6, 13.2, and 13.7 mm		
Optic Shape	Anterior: convex (toric convex as appropriate) Posterior: concave		
Haptics	Plate haptics with four foot plates and two (2) 0.36 mm diameter orientation partial depth ports	Plate haptics with four foot plates and two (2) 0.36 mm diameter orientation through ports	
Diopter Range	-3.00 D to -16.00 D (0.50 D steps)	-3.00 D to -16.00 D (0.50 D steps)	-3.00 D to -14.00 D (0.50 D steps)

Lens Feature	Approved in the US	Investigational Study CP19-01 EVO/EVO+ lenses	
	MICL (P030016), TMICL (P030016/S001)	VICMO, VTICMO	VICM5, VTICM5
Cylinder Diopter Range (Toric Only)	+1.0 D to +4.0 D (0.5 D steps)		

4.1.1 Instructions for Use and Administration

Surgery to implant the EVO/EVO+ lenses will be performed in accordance with instructions provided in Appendix B.

4.1.2 Storage Requirements

The study lenses are to be stored at room/ambient temperature. The storage location at the clinical site must have limited access, available to study site personnel only.

4.2 Treatment Replacement

A supplemental lens will be provided for each eye. Study lens accountability should be maintained as described in Section 4.5.

4.3 Other Materials

STAAR will provide the following materials:

- Supplemental lens for each study lens ordered,
- MICROSTAAR™ injector MSI-PF or MSI-TF reusable injector,
- SFC-45, single use cartridge for each study lens ordered,
- Foam tip plunger (FTP) for each study lens ordered, and
- 2% HPMC ophthalmic viscosurgical device (OVD)

4.4 Packaging and Labeling

Study lenses will be packaged in a glass vial, sealed in a polycarbonate tray with Tyvek lid placed in a white box, similar in shape and size to commercial product but without commercial artwork.

The visible information at the outer box level will include the following information:

- Sponsor name and address
- Study number
- Model number
- Serial number

- Dioptic power
- Expiration date
- Storage conditions
- Caution statement: e.g., “For clinical trial use only”, “Investigational Device. Limited by Federal (or United States) Law to Investigational Use”, etc.

The tray label will contain the following information:

- Sponsor name and address
- Study number
- Model number
- Serial number
- Dioptic power
- Storage conditions
- Caution statement: e.g., “For clinical trial use only”, “Investigational Device. Limited by Federal (or United States) Law to Investigational Use”, etc.

4.5 Accountability

The Investigator will be responsible for keeping current and accurate records of all study lenses received, dispensed, and returned to the Sponsor. The study lenses must be stored under the appropriate conditions in a secure, limited access area and are to be implanted only in subjects enrolled in the study, in accordance with the conditions specified in this protocol.

At time points throughout the study and/or upon completion of the study, the Sponsor/Sponsor's representative will review and verify the Investigator's accountability records. Following verification, and as directed by the Sponsor, all unused or explanted study lenses must be returned to the Sponsor.

[figure not shown]
4.6 Risk Assessment

Risk management is conducted in accordance with the principles described in ISO 14971:2012.

[REDACTED]

[REDACTED]

[REDACTED]

If new information regarding new risks to patients is made available during the course of the study, the IRB and applicable regulatory agencies will be notified, the informed consent will be updated, and the Investigator will be required to provide new information to patients and have them sign the revised ICF.

5.0 STUDY CONDUCT

5.1 Study Visits

All Subjects who meet the eligibility criteria will be seen according to the following schedule for each implanted eye:

VISIT	TIMING* (for each implanted eye)
• Preoperative Visit	Days -120 to -1
• Operative Visit	Day 0
• Postoperative Visit 1	1 day
• Postoperative Visit 2	5 – 9 days
• Postoperative Visit 3	21 – 35 days
• Postoperative Visit 4	70 – 98 days
• Postoperative Visit 5	147 – 182 days
• Postoperative Visit 6	330 – 420 days
• Postoperative Visit 7	690 – 810 days
• Postoperative Visit 8	1050 – 1170 days

* based upon days from surgery for each eye. Postoperative visits for both eyes may be scheduled on the same day only if visit window for each eye allows.

Following identification of a potential subject, the Investigator (or designee) will explain the purpose of the study, procedures, risks/benefits, and subject responsibilities to the potential subject. The subject will be provided a copy of the IRB approved consent form and a copy of the Patient Information Booklet for the appropriate FDA approved parent model. The subject's willingness and ability to meet the follow-up requirements of the study will be determined. If the subject chooses to participate in the investigation, written informed consent will be obtained. The subject and the person obtaining written consent, will sign and date the IRB approved ICF. The original signed document will be retained in the subject records, and a copy will be provided to the subject. In addition, the applicable privacy regulation requirements must be met.

5.1.1 Preoperative Visit – Days -120 to Day -1

Prospective subjects who have provided informed consent will be screened to determine eligibility for implantation of study lenses in one or both eyes. Demographic information, relevant ocular medical history, and current ocular medication use will be collected. The preoperative clinical evaluation will consist of a complete ophthalmic examination conducted no more than 120 days prior to surgery. Determination of eligibility will include consideration of all inclusion and exclusion criteria, including preoperative ECD as measured by the central reading center, calculation of the appropriate spherical and cylindrical lens power and size as provided by the STAAR OCOS system, and the opportunity for prospective subjects to experience their correction in the event that postoperative cylindrical refractive error of ≥ 1 D is predicted.

Refer to Appendix A: Schedule of Visits and Parameters for assessments to be performed.

5.1.2 Operative Visit – Day 0

Subjects will be reassessed to confirm eligibility. In addition, any changes in concomitant medications or AEs will be recorded. If the subject no longer meets eligibility criteria, he/she will be considered a screen failure. If the subject is eligible, he/she will be enrolled in the study and undergo surgery according to the surgical procedure described in Appendix B. If the study lens is not implanted due to a surgical complication, the subject will be discontinued from the study.

At approximately 1-6 hours after surgery, an intraocular pressure (IOP) reading in the implanted eye will be conducted. Any complications, AEs, or associated treatment given will be appropriately documented and reported.

For subjects who qualify to participate bilaterally, fellow eye implantation will occur between 7 days and 14 days after uneventful surgery in the first eye. If, in an Investigator's medical judgment, second eye surgery should be postponed to a date more than 14 days from primary eye implantation due to a safety concern, the Medical Monitor's approval for second eye surgery will be required.

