5.1.3 Postoperative Visits – Day 1 to Day 1170

Each treated eye will be seen for 8 postoperative visits according to the schedule in Appendix A. Postoperative visits for both eyes may be scheduled on the same day only if the study visit window for each eye allows.

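### Sections 5.1.2, 3.2.3 and 5.1.3 conflict on whether an already implanted primary eye stays in follow-up when fellow-eye implantation fails because of a surgical complication

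*Combined protocol and SAP*

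**What the plan says.** Three sections of the combined protocol and SAP bear on a failed implantation.

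- **Section 5.1.2 (Operative Visit):** "If the study lens is not implanted due to a surgical complication, the subject will be discontinued from the study". The rule is mandatory, acts on the subject rather than the eye, and makes no exception for a subject who already carries a study lens. A later paragraph of the section places fellow-eye surgery 7 to 14 days after an uneventful first operation, or later with the Medical Monitor's approval.
- **Section 3.2.3 (Subject Discontinuation):** "A subject may be discontinued (at the discretion of the Investigator, the Sponsor and/or the IRB) prior to the final study visit". One listed reason is a "surgical complication preventing implantation of the study lens in any eye". Before discontinuation, sites should try to "schedule a final study visit, and obtain as much follow-up data as possible". Afterwards, "Discontinued subjects should be followed outside of the study protocol", and "Subjects who are discontinued from the study following treatment will not be replaced".
- **Section 5.1.3 (Postoperative Visits):** "Each treated eye will be seen for 8 postoperative visits according to the schedule in Appendix A".

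Section 3.2 allows implantation in one eye or both. Section 7.3 puts every implanted eye in the safety population and rules out imputation. Section 7.4 bases the primary analysis on at least 300 primary eyes that have completed Visit 5.

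**The concern.** Visits, windows and endpoints are organised by eye, but the exit rule for a failed implantation is written by subject. In a bilateral subject the primary eye is already implanted when the fellow eye is operated on. If that second implantation fails, one section requires the subject to leave, another permits it, and a third says the implanted eye will be seen eight times. Sites could handle the same event differently and each be able to cite the protocol.

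The main stake is safety information on an eye that still carries the investigational lens. Primary eyes alone supply the primary endpoints in section 7.1.1. Under Appendix A the first postoperative specular microscopy and gonioscopy are at Visit 5, and the first postoperative lens grading, vault measurement and dilated fundus examination are at Visit 3. A primary eye that exits around the time of fellow-eye surgery would have no scheduled postoperative value for any of these.

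**Working it through.** **1. The sections side by side, for a primary eye implanted on Day 0 and a failed fellow-eye implantation**

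| Section | Unit | Force | Consequence for the primary eye |
|---|---|---|---|
| 5.1.2 | subject | mandatory | leaves the study, if the sentence reaches the second operation |
| 3.2.3 | subject | discretionary | may leave or stay |
| 5.1.3 | treated eye | mandatory | seen for eight visits |

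Two points suggest that 5.1.2 can reach the fellow eye. Section 5.1 sets out the visit schedule, including the Operative Visit, for each implanted eye. Section 3.2.3 refers to any eye for failed implantation, whereas its post-explant safeguard depends on both lenses: "If both EVO/EVO+ study lenses are explanted, a minimum of one post-explant visit should be completed".

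**2. What a literal exit would lose**

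The planned time of fellow-eye surgery is Day 7 to 14 of the primary eye. Visit 3 is Day 21 to 35 and Visit 5 is Day 147 to 182. An exit at the planned time removes Visits 3 to 8. A final visit at about two weeks could not stand in for Visit 5 ECD or for Visits 6 to 8. Section 3.2.3 names endothelial cell count as a final assessment only in the double-explant case.

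**3. The plan's own figures (section 7.2)**

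- Enrolment: 300 / 0.9 = 333.3, which agrees with 333.
- Case limit with n = 300 and rate 0.003: P(X ≥ 3) = 0.063 and P(X ≥ 4) = 0.013. A maximum of 3 cases fits a one-sided 5% level. That level is an assumption, because the plan does not state it.
- Detection of a 1% adverse event: 1 − 0.99^300 = 0.951, as stated.

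**4. Size of the loss**

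The documents give no rate of failed fellow-eye implantation. Let f be that rate and assume all 333 subjects are bilateral. Expected primary eyes lost = 333 × f. Visit 5 completers are shown under two readings of the 10% per year loss: a flat 10%, (333 − 333f) × 0.9, and prorated to Day 182, (333 − 333f) × 0.9^(182/365).

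| Assumed f | Eyes lost | Completers, flat 10% | Completers, prorated |
|---|---|---|---|
| 0 | 0 | 299.7 | 316.0 |
| 0.5% | 1.7 | 298.2 | 314.4 |
| 1% | 3.3 | 296.7 | 312.8 |
| 2% | 6.7 | 293.7 | 309.6 |
| 5% | 16.7 | 284.7 | 300.2 |

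Under proration, completers fall below 300 only if f exceeds 1 − 300/315.96 = 5.05%. Under a flat 10% there is no reserve even at f = 0.

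**5. Effect on the test**

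At the same assumed 5% level the limit stays at 3 cases from n = 280, where P(X ≥ 4) = 0.011, to n = 333, where it is 0.019.

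**The case against.** The strongest reply is that 5.1.2 concerns only the first operation. Its sentences run in order: eligibility is rechecked, the eligible subject is enrolled and operated on, and failure to implant leads to discontinuation. A subject is enrolled once, and the fellow eye appears only in a later paragraph with no exit rule of its own. In 3.2.3, *any eye* could also mean that no eye was implanted. The same section uses *any* in that sense in its replacement rule, and its explant wording refers to both lenses. One-eye participation is allowed, so a subject whose fellow-eye implantation fails still fits the design.

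This reading is tenable, and it means the text does not establish that an implanted eye will be dropped. It does not remove the problem, because nothing in 5.1.2 confines the sentence to the first eye and no other section settles the case. It could also be said that any discontinuation overrides the visit schedule in 5.1.3. That is true, but here the trigger is an event in the other eye, and the sections disagree on whether exit is required.

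Three stronger readings are tempting and should not be drawn:

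- **That the eye loses all its primary endpoint data.** Iridotomy and adverse events up to exit are recorded, the eye remains in the safety population, a final visit is sought, and ongoing serious events and device effects are followed under section 6.3.4.
- **That an implanted subject could be relabelled a screen failure under 5.1.2.** That sentence comes before enrolment in the sequence.
- **That the iridotomy comparison would be biased.** The documents give no link between a fellow-eye surgical complication and pupillary block in the primary eye.

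**Conclusion.** The conflict in wording is real. For an implanted primary eye with a failed fellow-eye implantation, sections 5.1.2, 3.2.3 and 5.1.3 give three different answers. If 5.1.2 were applied literally, that eye would usually leave before Visit 3. Fellow-eye surgery postponed past Day 14 would move the exit later. The eye would contribute no scheduled postoperative ECD to the Visit 5 endpoint or to the three-year model, and nothing to Visits 6 to 8.

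The expected number is small: about 2 to 7 primary eyes for an assumed failure rate of 0.5% to 2%, with all subjects bilateral. Both the rate and full bilaterality are assumptions. The 3-case limit is unaffected, and a shortfall below 300 completers depends mainly on how the 10% annual loss is read. The point therefore rests on avoidable loss of ECD and long-term safety data and on inconsistent handling across sites, not on power or on the validity of the iridotomy test.

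**What to change.** Reconcile sections 5.1.2, 3.2.3 and 5.1.3 with one eye-level retention rule, for example: *Discontinuation from the study because of failed implantation applies only to a subject in whom no eye has received a study lens. If a study lens is already in one eye, that eye continues in scheduled follow-up through Visit 8 and is counted in the Visit 5 analysis.* Reword the listed reason in 3.2.3 to match.

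This governs data retention and changes no treatment. It needs a short amendment to existing text. The only continuing cost is the follow-up visits already planned for that eye.
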